In this study we aim to test the utility of an alternative compact system consisting of a modified Sony action camera and Epson augmented reality glasses to capture and project the images of the examination in the real-time, respectively. This design would allow more portable use of this examination virtually everywhere in the hospital setting e.g.: in the emergency and inpatient departments as well as in outreach services. In addition, this design can be very helpful for clinical care in underserved communities as well as in developing countries, where traditional endoscopic equipment may not be available or feasible to transport.

To our knowledge, no previous studies have evaluated the use of this technique in endoscopy in general, nor in nasal endoscopic examination. Therefore, this study represents a novel proof-of-concept exploration of a low-cost, portable alternative for nasal endoscopic imaging.

Hypothesis and/or Specific Aims or Objectives

This study aims to test the utility of this method of examination of the nasal cavity in patients with tearing to rule out endonasal causes of tearing.

Patients with tearing will undergo endoscopic examination with recording using the described system as well as examination and recording with a standard endoscopic system for comparison.

The quality of images of the described method will be compared to the standard endoscopic for resolution, quality and utility by three attendings with experience in endoscopic nasal examination.

The comparison will be for the images captured by the action camera and with the standard tower. The augmented reality glasses are just a means of seeing these pictures in the realtime but the quality of images in the AR glasses are not going to be compared to the standard tower.

Title: Portable Endoscopic Camera System Using Modified Action Camera for Endoscopic Sinunatal Examination
PI: [name]
Institution: University of Arkansas for Medical Sciences

Study Design and Procedures

This is a prospective, cross-sectional, non-interventional study designed to evaluate the image quality and clinical utility of a modified portable endoscopic imaging system compared to a standard hospital-based endoscopic tower.

Study Population and Setting

Patients presenting to the ophthalmology or otolaryngology clinics with complaints of tearing and requiring nasal endoscopic examination as part of their standard clinical evaluation will be invited to participate. No investigational or therapeutic procedures will be performed; all imaging will occur during routine endoscopic assessment.

Imaging Procedure

Each participant will undergo two sequential nasal endoscopic examinations during the same clinical visit:

1. Standard Endoscopic Examination: performed using the clinic's standard endoscopic tower system.
2. Modified Sony Action Camera System Examination: performed immediately afterward using the described portable imaging setup.

The following nasal anatomical locations will be imaged with both systems for comparison:

- Inferior meatus
- Inferior concha
- Middle concha
- Middle meatus
- Nasal septum
- Any identifiable nasal pathology (e.g., polyps, ulcers, mucosal thickening)

Each site will be recorded as short video clips and still images for later review and comparison.

Description of the Modified System

The Sony Action Camera was modified to allow direct coupling with a standard rigid nasal endoscope:

Title: Portable Endoscopic Camera System Using Modified Action Camera for Endoscopic Sinunatal Examination
PI: [name]
Institution: University of Arkansas for Medical Sciences

1. The native 180° wide-angle lens was replaced with a narrow-field 31° lens, enabling full-frame capture of the endoscopic image without peripheral distortion.
2. The camera housing was adapted by attaching a ¾-inch water pipe end connector, serving as a secure and stable mount for the endoscope eyepiece.

The modified system captures both video and still images. The standard endoscopic tower records video and stills per the clinic's routine workflow to serve as the comparator reference.

Integration of Epson Augmented Reality (AR) Glasses

The Epson augmented glasses will be used to provide real-time, heads-up visualization of the endoscopic feed from the modified camera system.

During the examination, the live endoscopic video stream will be displayed directly in the wearer's field of view through the transparent projection lenses of the AR glasses. This allows the examiner to maintain situational awareness of the patient while simultaneously viewing the nasal anatomy, potentially improving procedural ergonomics and mobility compared to viewing a fixed external monitor.

Use of the Epson AR glasses is limited to the examiner only (not the patient). They are used purely for image visualization and evaluation of workflow feasibility — not for any diagnostic or therapeutic intervention.

User Qualifications and Training

All examinations will be conducted by residency and fellowship trained otolaryngologists and oculoplastic surgeons with expertise in performing endonasal endoscopic examination.

Before study initiation, all investigators will attend a brief orientation and device training session (~30 minutes) covering assembly of the modified camera, Epson AR glasses, handling and sterilization procedures, and data transmission. No additional certification beyond standard clinical competency in endoscopy is required.

Study Population

Forty adults presenting with sinunatal and lacrimal tearing symptoms suggestive of nasolacrimal drainage obstruction or sinunatal disease in the outpatient ophthalmology or ENT clinic. All recruitment will occur during routine outpatient encounters; no patients will be contacted or identified prior to their scheduled clinical visit.

Title: Portable Endoscopic Camera System Using Modified Action Camera for Endoscopic Sinunatal Examination
PI: [name]
Institution: University of Arkansas for Medical Sciences

To determine eligibility, the provider (PI) will access information that is routinely available during standard outpatient care, including name, MRN, age, DOB, diagnosis, and any existing endoscopy orders. Accessing this information is part of the normal clinic workflow and will be used solely to confirm eligibility for this study. This information will not be stored or retained once eligibility is established.

Subjects that meet eligibility will be approached with the proposal to participate in this study on the date of their appointment after the rational of the study, benefits and risks are discussed. Patients who will accept to participate will be asked to sign this study's informed consent form.

Inclusion Criteria

- Adult patients (18 years and older) presenting with tearing suggestive of nasolacrimal drainage obstruction
- Adult patients presenting with sinunatal disease with clinical findings on endonasal examination.
- Adult patients who require a clinically ordered nasal endoscopic exam.

Exclusion Criteria

- Children (Under the age of 18)
- Patients with over secretory tearing.

Risks of the study

There is no more than usual risk of endoscopic nasal examination and the second set of images will require only an additional 3-5 minutes and will not require any additional topical lidocaine spray. The camera and the virtual reality glasses are not in direct contact with the patient. In addition, the camera will be covered by a sterile bag for additional protection of the patient. Another risk to study participants is the potential for loss of confidentiality of study data. Images of the patients will be deidentified and given a study code to protect patients' confidentiality. Measures to protect the confidentiality of study data will be implemented as described in the Data Handling and Recordkeeping section below.

Benefits of the study

There will be no direct benefits to the study participants; however, knowledge gained from the study could potentially benefit patients in the future who may benefit from this examination portable examination method. This design would allow more portable use of this examination virtually everywhere in the hospital setting e.g.: in the emergency and inpatient departments as well as in outreach services. In addition, this design can be very helpful for clinical care in underserved communities as well as in developing countries.

Title: Portable Endoscopic Camera System Using Modified Action Camera for Endoscopic Sinunasal Examination
PI: [name]
Institution: University of Arkansas for Medical Sciences

Data Handling and Recordkeeping

Data Elements and Timing of Collection

Each participant will undergo two sequential nasal endoscopic examinations during a single clinical visit. The standard endoscopic imaging will occur first, followed immediately by imaging using the modified Sony Action Camera system, requiring approximately 3–5 additional minutes.

The following data elements will be obtained for research purposes:

- Endoscopic video clips and still images of nasal anatomical sites (inferior meatus, inferior concha, middle concha, middle meatus, nasal septum, and any visible pathology such as polyps, ulcers, or mucosal thickening).
- A coded study ID (number) used to pair the modified-system recordings with the standard-system recordings for the same nasal side of the same participant.
- Image quality ratings assigned by three attending physicians using a 5-point Likert scale assessing resolution, quality, and clinical utility.
- No other demographic, clinical, or identifiable patient information (e.g., name, MRN, DOB) will be stored. The signed consent form will be retained separately in the sites regulatory binder as required by UAMS institutional policy, but will not be linked to study data.

Data Capture and Storage

Both the standard endoscopic tower and the modified portable system will record media for each specified location.

Source capture:

The modified Sony camera transmits recordings wirelessly to a secure, encrypted UAMS-device.

Standard tower images are stored on the institutional network per routine workflow.

Transfer and storage:

Study media will be exported, de-identified, and stored on a secure UAMS OneDrive folder accessible only to authorized study investigators. During the de-identification process, all direct and indirect identifiers will be removed, including patient name, date of birth, medical record number, encounter number, date of service, and any facial or other uniquely identifying features if present. Each file will be assigned a coded study ID and the link between this coded ID and the participants identity will not be maintained. A temporary linking log containing the study code and direct identifiers will be created for the purposes of confirming eligibility, tracking consent, and ensuring accurate file matching. This linking log will be stored separately

Title: Portable Endoscopic Camera System Using Modified Action Camera for Endoscopic Sinunatal Examination
PI: [name]
Institution: University of Arkansas for Medical Sciences

from all study data in a secure, encrypted, access-restricted UAMS One-Drive folder. Access will be limited to only PI and IRB approved study staff. Once all recordings have been verified and permanently de-identified, the link between the coded ID and the participants identity will be destroyed using UAMS-approved deletion methods preventing recovery. Only fully de-identified files will be retained and used for analysis.

De-identification and Coding

Before analysis, all recordings will be permanently de-identified to remove any HIPAA identifiers or metadata. Each image/video set will be assigned a numeric study code solely for matching the modified and standard system images from the same patient and same nasal side. No re-identification will be possible once coding is complete.

Data Evaluation

Three attending physicians experienced in nasal endoscopy will independently grade the anonymized images using a 5-point Likert scale (1 = useless to 5 = excellent). Grading will occur exclusively on coded media files, with no patient identifiers visible at any stage.

Statistical Analysis

All data analysis will be performed by researchers at the Jones Eye Institute (JEI), University of Arkansas for Medical Sciences. Analysts will have access only to de-identified images and coded data, with no links to patient identifiers.

Descriptive statistics (mean, median, and standard deviation) will be used to summarize image-quality scores from both the standard and modified endoscopic systems. Nonparametric tests, including the Wilcoxon signed-rank test, will be applied to compare paired image-quality scores between the two systems to determine whether the modified endoscopic exam performs better, equivalent, or worse than the standard exam. Inter-rater reliability among the three physician graders will be assessed using the Intraclass Correlation Coefficient (ICC).

A total of 40 participants will be enrolled. This sample size provides sufficient power for within-subject comparisons, allowing detection of meaningful differences in image quality while accounting for potential variability across raters and minor data loss.

Sample size justification

A total of 40 participants will be enrolled. This sample size is appropriate for a paired comparison study in which each participant provides image-quality scores for both the modified system and the standard endoscopic system.

Title: Portable Endoscopic Camera System Using Modified Action Camera for Endoscopic Sinunasal Examination
PI: [name]
Institution: University of Arkansas for Medical Sciences

The primary analysis will use the Wilcoxon signed-rank test, which is commonly used for paired ordinal data. A formal power analysis for the Wilcoxon test will be completed by a statistician during the final analysis phase. However, based on typical assumptions used for paired nonparametric tests, a sample of 40 paired observations is generally sufficient to detect a small/moderate difference in Image quality with acceptable statistical power (80%) at the standard $\alpha=0.05$ level.

The sample size also provides a buffer for minor variability in image quality ratings across raters. Overall, enrolling 40 participants is expected to provide sufficient data to compare the two imaging systems.

Data Retention and Disposal

All study data will remain de-identified throughout the research process.

Retention: De-identified image sets and scoring data will be retained in a secure, password-protected UAMS cloud for seven years in accordance with institutional policy for research record retention.

Future use: The research team will not use the collected data for any future research projects.

Destruction: After seven years, data will be permanently destroyed in accordance with UAMS-institutional policy.

Ethical Considerations

This study will be conducted in accordance with all applicable government regulations and University of Arkansas for Medical Sciences research policies and procedures. This protocol and any amendments will be submitted and approved by the IRB as required.

Participation in this study involves a few minutes of additional time on the patient during their visit. No compensation is going to be offered to the study participants.

The informed consent and HIPAA authorization of each subject, using IRB-approved consent materials, will be obtained before that subject begins any study procedures. All subjects for this study will be provided a consent form on paper describing this study in language understandable to the study population. Consent materials will provide sufficient information for subjects to make an informed decision about their participation in this study. The person obtaining consent will thoroughly explain what the subjects need to know about the study, including study requirements and study risks and benefits. The consent process will take place during their clinic visit in the exam room. Participation privacy will be maintained and questions regarding participation will be answered. No coercion or undue influence will be used in the consent process.

This consent form must be signed by the subject or legally authorized representative and the person obtaining the consent. The participant will receive a paper copy of the signed consent

Title: Portable Endoscopic Camera System Using Modified Action Camera for Endoscopic Sinunusal Examination
PI: [name]
Institution: University of Arkansas for Medical Sciences

form, and the informed consent process will be documented in the research record.

Dissemination of Data

Results of this study may be used for presentations, posters, or publications. The publications will not contain any identifiable information that could be linked to a participant.

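### Graders are masked to patient identity only; nothing in the available text masks them to the imaging system, although the only listed outcome is a subjective 1–5 rating

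*Combined protocol and SAP*

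**What the plan says.** **Grading.** Data Evaluation: "Three attending physicians experienced in nasal endoscopy will independently grade the anonymized images using a 5-point Likert scale", followed by "Grading will occur exclusively on coded media files, with no patient identifiers visible at any stage".

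**Coding.** Data Capture and Storage: "Each file will be assigned a coded study ID". De-identification and Coding says each image or video set is "assigned a numeric study code solely for matching the modified and standard system images". Data Elements and Timing of Collection describes the same code: "A coded study ID (number) used to pair the modified-system recordings with the standard-system recordings". Identifiers and metadata are to be removed, and the media are kept in a folder open to authorized investigators.

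**Outcome.** Apart from the media and the study ID, the one listed data element is "Image quality ratings assigned by three attending physicians using a 5-point Likert scale assessing resolution, quality, and clinical utility". Under Statistical Analysis, these scores go into a Wilcoxon signed-rank test "to determine whether the modified endoscopic exam performs better, equivalent, or worse than the standard exam". Agreement between graders is assessed by an ICC.

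**Examiners.** User Qualifications and Training: "All examinations will be conducted by residency and fellowship trained otolaryngologists and oculoplastic surgeons with expertise in performing endonasal endoscopic examination". It does not say whether the graders are among them.

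The opening part of the document was not available for review, so statements about what is absent cover the remaining text.

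**The concern.** The two systems are compared only through opinion scores. If a grader knows which system produced a file, expectation about the new device or loyalty to the familiar tower can enter the score. When all three graders lean the same way, the paired difference shifts, and the signed-rank test cannot separate that shift from a real difference in image quality. The lean could run in either direction.

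No objective outcome is listed as a fallback. Scores already given cannot be masked afterwards. The image sets are retained for seven years, so a masked re-read within the study would be possible, but it would mean grading twice.

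**Working it through.** **1. What is concealed, and why**

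| Step in the plan | Stated or evident purpose | Hides the system? |
|---|---|---|
| Study code | Patient confidentiality; matching the two systems' files | No; it links the pair |
| Removal of identifiers and metadata | Privacy | Perhaps some device tags; not overlays, pairing or viewing order |
| Independent grading | Keeps graders apart from each other | No |
| No patient identifiers visible | Privacy | No |

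The paired analysis also needs a system label for every file. The plan does not say where that label is held or that graders do not see it.

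**2. The plan's own figure.** Sample size justification gives 40 pairs, 80% power and α = 0.05 for a small/moderate difference. It gives no numeric effect or SD, so the claim can be neither confirmed nor refuted. Taking two-sided α (assumed) and Wilcoxon efficiency 3/π, √(40 × 3/π) = 6.180. The detectable difference is (1.960 + 0.842)/6.180 = 0.453 SD of the paired difference. The masking point does not depend on this.

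**3. Preference shared by all three graders (sizes assumed).** With no true difference and a constant shift of b SDs, P(reject) ≈ Φ(6.180b − 1.960) + Φ(−6.180b − 1.960). At b = 0.3, 6.180 × 0.3 − 1.960 = −0.106, giving 0.458. Simulation (n = 40, normal differences, 20,000 runs):

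| b (SD) | Approximation | Simulated |
|---|---|---|
| 0 | 0.050 | 0.050 |
| 0.1 | 0.095 | 0.091 |
| 0.2 | 0.235 | 0.228 |
| 0.3 | 0.458 | 0.440 |
| 0.5 | 0.871 | 0.856 |

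The opposite error: if the portable system is truly 0.5 SD worse, a shared 0.3 SD preference for it cuts detection from 0.852 to 0.227.

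**4. Preference held by one grader.** The plan does not say how the three scores are combined. If they are averaged, a 0.3-point preference shifts the mean by 0.3/3 = 0.1 point. Rejection then runs from 7% to 23% as the SD of the paired difference falls from 1.5 to 0.5 points. A second model rounds scores to 1–5, with assumed SDs of 0.6 (patient), 0.4 (patient-by-system) and 0.5 (grader residual), and mean score 3 or 4.5:

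| One grader's preference | Mean 3 | Mean 4.5 |
|---|---|---|
| 0.3 points, scores averaged | about 13% | about 10% |
| 1 point, scores averaged | about 77% | about 44% |
| 0.3 points, that grader tested alone | about 46% | about 34% |

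**5. Does the ICC show it?** In the same model, a 0.3-point preference shared by all three graders moves the ICC from 0.601 to 0.608 (mean 3) and from 0.556 to 0.551 (mean 4.5). Rejection is 69% and 58%. Agreement is almost unchanged while the comparison is biased.

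**6. Partial masking.** If a shared 0.3 SD preference can act in only 25%, 50% or 75% of participants, rejection is 7%, 14% or 27%, against 44% when it acts in all. The documents give no basis for choosing among these.

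**The case against.** The strongest reply is that masking may achieve little here. Image appearance is what is rated, the portable camera has a replaced narrow-field lens, and experienced endoscopists may recognise the source. Covering overlays leaves frame shape and colour as cues. This stands: the gain is uncertain, the 44% and 85% figures are not the gain, and the plan needs a check on whether masking worked.

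A second reply is that direct comparison was intended. The aims section says the images will be compared with the standard system by three attendings, which is compatible with side-by-side viewing. Small differences may be harder to see unpaired, so this is a real cost. It does not remove the need to state the viewing conditions.

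A third is that this is a proof-of-concept study. That limits the severity, but the plan still draws a formal comparative conclusion and foresees publication.

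Readers might also infer more than the text supports:

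- **That graders will know the system, or will grade pairs side by side.** The plan is silent on both; these are gaps, not stated practices.
- **That graders are the examiners.** Overlap is neither shown nor excluded.
- **That a lean in one grader is harmless.** That holds only if the lean is small and the scores are averaged, as step 4 of the working shows.

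**Conclusion.** The gap is real and should be closed before grading starts. In the available text, masking covers patient identity only, and the conclusion rests wholly on subjective scores. Confidence that masking text is absent is high; confidence in the size of the gain from adding it is moderate.

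The documents give neither a preference size nor an SD, so every percentage above is illustrative and none is an error rate for this trial. The shared-preference figures assume a constant shift acting in all participants and a two-sided test. The documents do not support a conclusion that the results will be biased, or in which direction. They support the narrower one that, followed as written, the plan does not prevent such bias, and its ICC would not expose it if all three graders shared it. This is a cheap improvement rather than a fatal flaw.

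**What to change.** Add to Data Evaluation, before grading starts:

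- A study team member who does not grade gives each graded item a neutral code that reveals neither the system nor its pair. The protocol states whether an item is a file or a set.
- The key holds no patient identifier and is withheld from graders until all scores are locked. Until then graders have no access to the source-media folder and see only recoded copies.
- Items are shown unpaired, in computer-generated random order across patients and systems.
- Text or logo overlays that name the system are covered without altering resolution or field of view.
- Graders do not score media from participants they examined. If that cannot be arranged, the overlap is recorded under the study code before the linking log is destroyed, and a sensitivity analysis without those scores is reported.
- Each grader records a guess of the system after scoring each item.
- The report states that masking is incomplete.

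In De-identification and Coding, amend the limit on the code's purpose to allow the second code. In Data Elements and Timing of Collection, add the system guess and, if needed, the overlap flag.

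**Cost.** No new readers or patient procedures. Checking and recoding is per-file work whatever the grading unit: 40 participants × 2 systems × 5 sites × 2 media types = 800 files at least (one clip and one still per site, one side, before pathology), or about 1,600 if both sides are recorded. Side-by-side viewing is lost. If overlap occurs with one examiner per participant (assumption), the sensitivity analysis drops at most one of three scores. All 40 pairs remain, and in the rounded model the SD of the mean paired difference rises by about 10–11% (0.725 to 0.795, or 0.587 to 0.651).

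### The plan promises a verdict of better, equivalent or worse, but its only named comparison tests for a difference and cannot establish equivalence

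*Combined protocol and SAP*

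**What the plan says.** The Statistical Analysis section of the combined protocol and SAP applies nonparametric tests, with the Wilcoxon signed-rank test as the one example, to paired scores from the two systems "to determine whether the modified endoscopic exam performs better, equivalent, or worse than the standard exam". The Sample size justification section confirms its status: "The primary analysis will use the Wilcoxon signed-rank test, which is commonly used for paired ordinal data".

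The other planned analyses are summaries and a reliability measure. "Descriptive statistics (mean, median, and standard deviation) will be used to summarize image-quality scores from both the standard and modified endoscopic systems". An intraclass correlation coefficient is planned for agreement among the three graders.

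The sample size is argued only in terms of finding a difference: "a sample of 40 paired observations is generally sufficient to detect a small/moderate difference in Image quality with acceptable statistical power (80"%) at α = 0.05. The unit is the participant: "each participant provides image-quality scores for both the modified system and the standard endoscopic system".

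No section gives an equivalence or non-inferiority margin, a confidence interval for the paired difference, a definition of equivalence, or a second comparative test.

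**The concern.** The null hypothesis of the signed-rank test is that paired scores do not shift between systems. Rejecting it, and looking at the direction, supports better or worse. Failing to reject it says only that the data did not exclude zero, which can happen because the systems are close or because the data are too few or too noisy. Without a margin there is nothing to be equivalent within, so no test could supply the third verdict.

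The likely way to fill the gap is to read p > 0.05 as equivalent. That reading rewards poor data: noisier grading and lost pairs both make the favourable verdict more likely for a camera that is truly worse. Comparing images with the standard tower is the study's stated purpose and publication is foreseen, so the mislabelled result would be the main one.

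**Working it through.** **1. Inputs.** From the documents: 40 pairs, α = 0.05, 80% power, a 1-to-5 scale. Not in the documents, so assumed: a two-sided test, a true deficit of 0.5 points, and SDs of the paired difference of 0.5, 0.75, 1.0, 1.2 and 1.5. One score per participant per system is also assumed, matching the plan's own count of 40 pairs.

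**2. The plan's own figure.** No effect size or SD is given, so 40 pairs cannot be reproduced directly. Solving backwards, with 3/π as the efficiency of the signed-rank test under normality:

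detectable difference in SDs = (1.960 + 0.842) / √(40 × 3/π) = 2.802 / 6.180 = 0.45.

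The claim of 80% power therefore holds for differences of about 0.45 SD. It concerns detecting a difference and says nothing about showing equivalence.

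**3. If non-significance were read as equivalent.** The approximate chance of a non-significant result is 1 − Φ(δ/SD × √(n × 3/π) − 1.960). For δ = 0.5, SD = 1.0 and n = 40 this is 1 − Φ(3.090 − 1.960) = 1 − Φ(1.130) ≈ 13%. Simulation of the test itself (20,000 runs per scenario, normal differences) gives slightly higher values:

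| SD of paired difference | 0.5 | 0.75 | 1.0 | 1.2 | 1.5 |
|---|---|---|---|---|---|
| Non-significant, 40 pairs | 0.0% | 1.8% | 14.5% | 28.9% | 48.5% |
| Non-significant, 36 pairs (10% loss assumed) | 0.0% | 3.2% | 18.8% | 33.7% | 52.8% |

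At a true difference of 0.5 SD, the non-significant share is about 72% with 10 pairs, 46% with 20, 14.5% with 40 and 1% with 80. The smaller the study, the easier the favourable verdict.

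**4. Does the bounded, tied scale change this?** Integer 1-to-5 scores were simulated with a true mean gap of −0.5, zero differences dropped and ties corrected.
- Tower in mid-scale (latent mean 3.5), SDs of 0.73, 1.02, 1.20 and 1.52: non-significant in 1%, 15%, 29% and 49%.
- Tower near the ceiling (latent mean 4.25), SDs of 0.71, 0.96, 1.12 and 1.41: 1%, 12%, 22% and 42%.

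The pattern is the same.

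**5. What 40 pairs can deliver instead.** The half-width of a 95% interval for the mean paired difference is 2.023 × SD / √40 = 0.16, 0.24, 0.32, 0.38 and 0.48 points at the five SDs.

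For an equivalence claim, the 90% interval must lie inside the margin. With truly equal systems and two illustrative margins:

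| SD of paired difference | 0.5 | 0.75 | 1.0 | 1.2 | 1.5 |
|---|---|---|---|---|---|
| Equivalence shown, margin 0.5, 40 pairs | 100.0% | 98.7% | 85.6% | 65.5% | 33.1% |
| Pairs for 80% chance, margin 0.5 | 11 | 21 | 36 | 51 | 79 |
| Equivalence shown, margin 0.25, 40 pairs | 85.6% | 33.1% | 3.0% | 0.1% | 0.0% |
| Pairs for 80% chance, margin 0.25 | 36 | 79 | 139 | 199 | 310 |

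The sharp fall is simple to see. At SD 1.0 the 90% half-width averages about 1.685 / √40 = 0.27 points, already wider than a 0.25-point margin.

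**The case against.** The strongest case is that this is loose wording in a small study. The word appears once, in a purpose clause. The aims state no equivalence hypothesis, the study is described as a proof of concept, no clinical decision hangs on the verdict, and means and medians will stand beside the p-value. The plan names the Wilcoxon test only as an example, so other tests are not excluded. All of that is true and limits the harm. It does not supply a route to the verdict: the clause states what the comparison is meant to decide, and without a margin no further test would help.

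The error rates also depend on assumptions and run from 0% to 48.5%. This stands. Moreover, the ratings come from three attendings on three attributes ("Image quality ratings assigned by three attending physicians using a 5-point Likert scale assessing resolution, quality, and clinical utility"), over several sites ("Both the standard endoscopic tower and the modified portable system will record media for each specified location") and by nasal side ("matching the modified and standard system images from the same patient and same nasal side"). If these are averaged into one score, the SD would normally be lower than for a single rating, which makes the upper end less likely. The documents do not settle this. The defect itself does not depend on the SD.

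An interval for the mean is not the only choice: a Hodges-Lehmann interval would match the signed-rank test more closely. Either would serve. In the integer-score simulation the 95% interval for the mean covered the truth in 94.9% to 95.2% of runs. Finally, an interval computed on pooled site-level or rater-level pairs would generally be too narrow. The plan's own sizing, however, is one pair per participant, and that is the unit meant here.

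**Conclusion.** The concern holds. The flaw is in the plan as written: it commits the primary comparison to three possible conclusions and provides a valid method for two. The plan nowhere equates p > 0.05 with equivalence, but it offers no other basis for that verdict.

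The practical size is uncertain. For an assumed 0.5-point deficit, the wrong verdict would be negligible at SDs up to 0.75 and would affect roughly one study in seven at SD 1.0 and nearly half at SD 1.5. These figures assume one normal paired difference per participant and are illustrations. The consequence is confined to the validity of the reported conclusion. It should be corrected before grading starts, since a rule or margin chosen after the scores are seen would be open to bias.

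**What to change.** **Preferred.** Delete the word *equivalent* from the purpose clause, keep the Wilcoxon test for better or worse, and add: *The mean paired difference behind each test will be reported with its 95% confidence interval. A non-significant result will not be taken to show equivalence.* The interval should use the unit on which the study is sized, one pair per participant. Cost: one word removed and two sentences added, with no extra patients or data whatever the SD.

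**Alternative, only if the sponsor wants an equivalence claim, and before any grading:**
1. Define the single participant-level paired score across raters, attributes, sites and nasal sides.
2. Set a margin on the 5-point scale on clinical grounds.
3. Declare equivalence only if the 90% confidence interval for the mean paired difference lies inside the margin. If the Wilcoxon test is also significant, report the difference and its direction beside that verdict.
4. Otherwise report better or worse when the test is significant, and inconclusive when it is not.

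This route costs a score definition and a margin decision, and may cost patients. At SD 1.0 with truly equal systems and 40 pairs, the result would be inconclusive in about 10% of studies at a 0.5-point margin and about 92% at 0.25. The sample size would have to be justified again for the chosen margin.
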